6.13.2 Severity Assessment

Adverse events will be classified by the Investigator as mild, moderate, severe, life-threatening or fatal, as defined below. When the severity of the AE changes over time, the change in severity will be recorded on the AE eCRF as a new AE, and the original AE will stop when the new AE starts

Table 5 Adverse Event Severity Definitions

Classification	Definition
Mild	Mild; asymptomatic or mild symptoms; clinical or diagnostic observations only; intervention not indicated
Moderate	Moderate; minimal, local or noninvasive intervention indicated; limiting age-appropriate instrumental ADL^a
Severe	Severe or medically significant but not immediately life-threatening; hospitalization or prolongation of hospitalization indicated; disabling; limiting age-appropriate self-care $\mathrm{ADL}^{\mathrm{b}}$
Life-threatening	Life-threatening consequences; urgent intervention indicated
Death	Death related to AE

^a Instrumental ADL refers to preparing meals, shopping for groceries or clothes, using the telephone, managing money, etc.

ADL = activities of daily living; AE = adverse event.

Source: CTCAE, Version [4.03].

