9.11.1 Adverse Event Analyses

Adverse events will be mapped to system organ classes and preferred terms using the Medical Dictionary for Regulatory Activities (MedDRA).

The subject incidence of TEAEs, TEAEs related to study drug, SAEs, AEs leading to discontinuation, and fatal AEs will be summarized. This overall summary will also provide TEAEs by maximum severity.

The subject incidence of TEAEs, TEAEs related to study drug, AEs, and AEs leading to discontinuation will also be presented by system organ class and preferred term. Preferred term summaries may also be provided.

A TEAE is defined as an AE that either began after the first study drug dose or worsened after the first dose. In summarizing the subject incidence of AEs, multiple events with the same preferred term or with increases in severity will only be counted as one AE and summarized at the maximum severity. Subject incidence is similarly defined for multiple events within the same system organ class. Summaries by period will be based on AEs considered emergent within a period.

Adverse events occurring after a subject has completed the Main Study and prior to the Open-Label Extension Period will be recorded as medical history. Adverse events occurring after first dose of study drug in the Open-Label Extension Period will be considered treatment emergent.

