### 9.9.1. ADVERSE EVENTS

AEs will be coded to SOC and PT using the MedDRA dictionary, version 19.1 and will be classified as follows:

- **Prior AEs** are defined as AEs that started on or after the signature of the Main Study informed consent but prior to the first dose of OL OTTP study drug;
- **For the overall summaries**, (TEAEs) are defined as any AEs that started or worsened in severity on or after the first dose of Open-Label study drug up to the last dose of study drug during the Open-Label Optimized Treatment and Titration period, Open-Label Stable-Dose Period, Double-Blind Randomized-Withdrawal Period or Open-Label Extension period (whichever is the latest) + 30 days.
- **For the DB RWP**, TEAEs are defined as any AEs that started or worsened in severity on or after the first dose of double-blind study drug up to 1) the last dose of double-blind study drug for subjects who did not enter the Open-Label Extension, 2) the first dose of study drug during the Open-Label Extension for subjects who rolled over into the Open-Label Extension immediately

after having completed the Main Study or 3) whichever occur first between the following two timepoints for subjects who rolled over into the Open-Label Extension after having re-entered into the study: last dose of double-blind study drug or first dose of study drug during the Open-Label Extension.

- **For the Main Study**, TEAEs are defined as any AEs that started or worsened in severity on or after the first dose of study drug up to the first day of the Open-Label Extension period for rollover subjects; or the first day of the Open-Label Extension period or the day of the last dose of study drug in the Double-Blind Randomized-Withdrawal period + 30 days (whichever is the earliest) for re-entry subjects.
- **For the OLE**, TEAEs are defined as any AEs that started or worsened in severity on or after the first dose of Open-Label study drug during the Open-Label Extension period up to the last dose of study drug + 30 days.
- **Post AEs** are defined as any AEs that started or worsened in severity after the last dose of study drug during the OTTP, SBP, RWP or OLE (whichever is the latest) + 30 days.

For OLE re-entry subjects, AEs occurring after their last dose of DB study drug, but prior to their first dose of OLE study drug will be considered as post AEs .

Only TEAEs will be summarized, but all AEs will be presented in the subject data listings.

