#### **9.9.1.1. All TEAEs**

Subject incidence of TEAEs will be summarized in 2 separate tables by:

- SOC and PT
- PT only

If a subject reports a TEAE more than once within a SOC or PT, the TEAE will be reported only once for that SOC or PT.

For summaries by SOC and PT, SOC's will be sorted in alphabetical order and PT's within each SOC in

descending order of overall frequency. For summaries by PT only, PTs will be sorted in descending order of overall frequency.

Subject incidence of TEAEs presented by SOC and PT will be broken down further by maximum severity (refer to section 9.9.1.2) and worst relationship to study drug (refer to section 9.9.1.3). Handling of missing or partially missing start and stop dates for TEAEs are described in **Error! Reference source not found..**

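### An AE that eases during a study period gets a new record and, read literally, is counted as a new treatment-emergent event of that period and of the arm received

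*SAP*

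**What the plan says.** **Recording.** Protocol 6.13.2: "When the severity of the AE changes over time, the change in severity will be recorded on the AE eCRF as a new AE". The earlier record is closed at the point where its successor opens. The direction of the change is not restricted.

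**Counting.** SAP 9.9.1, double-blind period: "TEAEs are defined as any AEs that started or worsened in severity on or after the first dose of double-blind study drug". A start date in the window is sufficient on its own. The window closes at the last double-blind dose, or at the first extension dose for rollover subjects. The Main Study, extension and overall definitions in the same section use the same start-or-worsened form. SAP Appendix 2 applies it by comparing the AE's start date with the first dose date. Protocol 9.11.1 agrees: "A TEAE is defined as an AE that either began after the first study drug dose or worsened after the first dose", and "Summaries by period will be based on AEs considered emergent within a period".

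**Merging.** Protocol 9.11.1 says that "multiple events with the same preferred term or with increases in severity will only be counted as one AE". SAP 9.9.1.1 says that, for a subject with repeats, "the TEAE will be reported only once for that SOC or PT".

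**Attribution.** Under SAP 5.3, double-blind safety summaries classify subjects by the treatment they actually received.

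**The concern.** A record opened because an AE improved has a start date like any other. If that date falls in the double-blind period, the counting rule accepts it as emergent, although nothing new has happened and nothing has worsened. No section compares the record with the one it replaces.

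The design makes this more than a clerical matter. Randomized subjects have had 14 weeks of JZP-258 (12 of titration and 2 at stable dose), and half are then switched to placebo. Protocol 6.13.4 treats improvement on stopping the drug as evidence that an AE was drug-related, yet the counting rule would enter the same improvement as a new placebo event. If the continuation record keeps a related rating, it also enters the related-TEAE count for placebo.

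The double-blind table is the only randomized safety comparison. It will be read closely, because Protocol 3.1.3 cites a higher (not statistically significant) AE count on placebo in the previous Xyrem withdrawal study when justifying this design.

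**Working it through.** The plan states no figure on this point, so there is none to reproduce. The check applies the rules to test cases and then scales the result.

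**1. Step-down across the boundary.** A moderate AE begins on open-label JZP-258, 20 days before the double-blind period. It eases to mild on double-blind day 3 on placebo and ends on day 10. Protocol 6.13.2 yields two records:
- A: moderate, start day −20, stop day 3
- B: mild, start day 3, stop day 10

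SAP 9.9.1 with a window of days 1 to 14: A starts outside the window and did not worsen in it, so it is not emergent. B starts inside it, so it is emergent. Count: 1 placebo TEAE. If B counts only when its severity exceeds the severity at the start of the period, mild does not exceed moderate. Count: 0.

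**2. Do the merging rules remove B?** They combine records that are in the same summary. A is not in the double-blind summary, so B stands alone and stays. Had the AE begun on day 2 and eased on day 5, both records would be in the table under one preferred term and would count once. The gap is therefore at the period boundary, not within a period.

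**3. Other boundaries.**
- *Day 1:* an AE that began after consent but before the first dose is a prior AE. If it eases after dosing, its second record is a TEAE.
- *Extension entry:* an AE from the Main Study that eases after the first extension dose becomes an extension TEAE on JZP-258. This error counts against JZP-258.
- *Overall and Main Study summaries:* for an AE that first arose on open-label JZP-258, the first record is already a TEAE and the preferred term counts once, so nothing is added. SAP 9.9 also removes placebo-phase data from the across-period summaries.

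**4. Which reference severity?** Take an AE that is severe in titration, mild at the end of the Stable-Dose Period and moderate after randomization. Against the severity at the start of the period, moderate exceeds mild and the AE counts. Against the highest severity ever recorded before the period, moderate does not exceed severe and a genuine worsening disappears.

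**5. Size.** With the planned 65 per arm (Protocol 9.3), one affected subject adds at most 1/65 = 1.5 percentage points to any-TEAE incidence. It adds nothing to that line if the subject has another double-blind TEAE.

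Any total needs assumptions that the documents do not supply. Let q be the share entering the double-blind period with an ongoing AE above mild, and e the share of those that ease while still ongoing. Spurious incidence is q × e, before allowing for subjects already counted.

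| Assumed q | Assumed e, placebo / JZP-258 | Placebo | JZP-258 |
|---|---|---|---|
| 2% | 50% / 10% | 1.0% (0.7 of 65) | 0.2% (0.1 of 65) |
| 5% | 50% / 10% | 2.5% (1.6 of 65) | 0.5% (0.3 of 65) |
| 15% | 80% / 20% | 12.0% (7.8 of 65) | 3.0% (2.0 of 65) |

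The last row is an outer limit, not an expectation.

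**The case against.** **An event-level reading exists.** Since every worsening already opens a new record, the words about worsening would be redundant if any record start counted. Reading AE as the clinical event gives those words a purpose and excludes improvements. This is a fair argument, but Protocol 6.13.2 itself calls the record a new AE, and Appendix 2 works from start dates. A programmer following the text would count it.

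**The numbers are probably small.** This stands. Randomization requires that, in the Investigator's judgment, no clinically significant AE due to JZP-258 has occurred, and it follows at least four weeks on an unchanged, tolerated dose. Protocol 1.3.4.3 says Xyrem reactions tended to come early and diminish. A mild AE that ends opens no second record. With a mean half-life near 0.57 hour (Protocol 1.4.1), complete resolution after withdrawal is at least as plausible as a lingering step-down.

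**The consequence is limited.** This also stands. Safety analysis is descriptive, all AEs are listed, and no efficacy result or error rate depends on it. But a descriptive table has no other safeguard, and readers use the table rather than the listing.

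**Stronger readings to resist.** A reader might infer a known bias of several percentage points in favour of JZP-258. The documents give neither the carry-over rate nor the step-down rates, so direction is a plausible inference and size is unknown. A reader might also infer that all TEAE tables are distorted, or that the merging rules ignore decreases altogether. Neither follows: the same-preferred-term clause covers step-downs within a summary, and the effect lies mainly in the by-period tables.

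**Conclusion.** Wrong as written. The recording rule and the counting rule together turn an improving AE into a new TEAE of the period in which it improves, and no rule in either document prevents it. The main effect is on the double-blind by-treatment tables, with lesser effects at Day 1 and extension entry.

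The rule applies to both arms. Greater inflation on placebo rests on the assumption that drug-related AEs ease more often once the drug is stopped. The size is at most 1.5 percentage points per affected subject at 65 per arm. The number affected is unknown and probably small, and it is zero if nobody carries an AE above mild into randomization. The correction is still worth making, because it is cheap and this is the only randomized safety contrast.

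**What to change.** In SAP 9.9.1 and Appendix 2, state that:
- a record opened only because severity changed is linked to the record it continues;
- such a record is treatment-emergent in a period only if the AE's first record started in that period, or if the new severity exceeds the severity at the start of the period, meaning the last severity before that period's first dose;
- a record opened by a decrease in severity is not newly emergent.

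Apply this to the double-blind, Main Study, extension and overall definitions. The reference should not be the highest severity before the period, for the reason in step 4 of the working. Under the proposed rule, an AE that eases and then returns only to its entry severity within the period is not counted, and the SAP should say so openly.

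Cost: SAP wording and a programming step that links contiguous records (same preferred term, stop date of one equal to start date of the next), with manual review of a few links before the soft lock. No new data are needed and patient care does not change.

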5.2 Selection and Timing of Dose for Each Subject

Sodium oxybate has a $t_{1/2}$ of approximately 0.5 to 1 hour. Pharmacologic doses of sodium oxybate have clinical sedative effects that typically last 2 to 4 hours. Sodium oxybate in divided nightly doses has been studied in patients with narcolepsy and patients with fibromyalgia.

Based on pharmacokinetic data demonstrating the generally similar mean concentration-time profiles for JZP-258 and Xyrem under the fasted condition with similar AUC, T_{max} and $t_{1/2}$, and FDA defined bioequivalence under fed conditions, the proposed dose range and timing of dosing of JZP-258 will be similar to Xyrem.

With the following exception, all groups should dose with JZP-258 orally in two equally divided doses taken at bedtime and again 2.5 to 4 hours later. Subjects who entered the study on Xyrem (Pre-randomization Groups 1 and 2) and have used a different nightly dosing regimen prior to study entry, may continue their prestudy dosing regimen throughout the study (i.e. the dosing regimen may consist of two or three equally or unequally nightly divided doses and dosing may begin after the first nightly awakening, however, a once nightly dosing will not be permitted during the study). Subjects entering the study on a different nightly dosing regimen may not change their regimen during the study.

Subjects in all groups will be instructed to take each dose while in bed and remain in bed after each dose. Subjects should take the first dose of study drug at least 2 hours after eating.

Investigators should caution subjects about operating hazardous machinery, including automobiles or airplanes, until subjects are reasonably certain that study drug does not affect them adversely (e.g., impair judgment, thinking, or motor skills). Subjects should not engage in hazardous occupations or activities requiring complete mental alertness or motor coordination, such as operating machinery or a motor vehicle or flying an airplane or going to school alone, for at least 6 hours after taking any dose of study drug.

Confidential Page 47 of 148

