**Table 1 Visit Windows for Assessments Recorded Daily**

Study Period	Adjusted-Defined Windows		Visit Windows
	Visit	Scheduled Period Day	
OL OTTP	Week 1	8	Study Day 1 < Period Day ≤ 8
	Week 2	15	9 ≤ Period Day ≤ 15
	Week 3	22	16 ≤ Period Day ≤ 22
	Week 4	29	23 ≤ Period Day ≤ 29
	Week 5	36	30 ≤ Period Day ≤ 36
	Week 6	43	37 ≤ Period Day ≤ 43
	Week 7	50	44 ≤ Period Day ≤ 50
	Week 8	57	51 ≤ Period Day ≤ 57
	Week 9	64	58 ≤ Period Day ≤ 64
	Week 10	71	65 ≤ Period Day ≤ 71
	Week 11	78	72 ≤ Period Day ≤ 78
	Week 12	85	79 ≤ Period Day ≤ Date of Visit 14

Statistical Analysis Plan

---

OL SDP	Week 1	8	1 < Period Day ≤ 8
	Week 2	15	9 ≤ Period Day ≤ Date of Visit 15
	Over Weeks 1 and 2	n/a	1 < Period Day ≤ Date of Visit 15
DB RWP	Week 1	8	1 < Period Day ≤ 8
	Week 2	15	9 ≤ Period Day ≤ Date of Visit 16
	Over Weeks 1 and 2	n/a	1 < Period Day ≤ Date of Visit 16

Note: DB: Double-Blind. n/a: Not Applicable. OL: Open-Label. OTTP: Optimized Treatment and Titration Period. RWP: Randomized-Withdrawal Period. SDP: Stable-Dose Period.

Note: Period Day 1 is excluded from the visit windows as the study drug will be taken only after all the assessments scheduled to be collected on that day will have been performed.

Note: For SDP longer or shorter than 14 days, use all available data from the period to calculate baseline, for DB RWP longer or shorter than 14 days, use all available data to account for efficacy.

For measurements/assessments other than cataplexy attacks, scheduled assessments will be summarized by nominal visits. Unscheduled and Early Termination visits will be mapped based on the scheduled Period Day of each visit with adjusted analysis-defined visit windows, unless otherwise specified. The adjusted analysis-defined windows are specified in [Table 2](#).

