**ALGORITHM FOR TREATMENT EMERGENCE OF ADVERSE EVENTS**

START DATE	STOP DATE	ACTION
Known	Known, Partial, Missing	
 
• If AE start date or worsened in severity < study drug first dose date, then not TEAE
 
• If study drug first dose date ≤ AE start date or worsened in severity ≤ (study drug last dose date + 30 days), then TEAE
 

Partial, but known components show that it cannot be on or after study drug first dose date	Known, Partial, Missing	Not TEAE
Partial, but known components show that it could be on or after study first dose date	Known	
 
• If AE stop date < study drug first dose date, then not TEAE
 
• If study drug first dose date ≤ AE worsened in severity or stop date ≤ (study drug last dose date + 30 days), then TEAE
 

or	Partial	If known components show that: 
 
• AE stop date < study drug first dose date, then not TEAE
 
• {[Study drug first dose date ≤ AE stop date ≤ (study drug last dose date + 30 days)] or [(study drug last dose date + 30 days) < AE stop date]}, then TEAE
 

Missing	Missing	Assumed TEAE

Note: Missing days will be assumed to be the first day of the month and missing months will be assumed to be the first month of the year for the purposes of determining if a partial date could be on or after the study first dose date (i.e. first day of month if day unknown or 1st January if day and month are unknown),.

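### SAP 9.9.1 has no same-day rule for period TEAEs: read by date, events on Visit 15 before the bedtime first blinded dose become double-blind (including placebo) TEAEs, and rollover events dated Visit 16 fall in two periods

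*SAP*

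**What the plan says.** **Opening of the double-blind window.** SAP 9.9.1: "TEAEs are defined as any AEs that started or worsened in severity on or after the first dose of double-blind study drug".

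**How emergence is decided.** For a known start date, SAP Appendix 2 calls an event treatment-emergent when "study drug first dose date ≤ AE start date or worsened in severity", with an upper bound 30 days after the last dose. Both sides are dates, and equality counts. SAP 6.1 also numbers double-blind days for safety data from the date of the first double-blind dose.

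**When drug is taken.** Protocol 5.2 has doses "taken at bedtime and again 2.5 to 4 hours later", apart from some Xyrem-experienced subjects who may keep a different regimen. In Protocol 7.1.4, AEs are recorded and vital signs, electrolytes, PHQ-9 and C-SSRS are obtained at Visit 15, the visit at which the subject is randomized and blinded drug is dispensed.

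**Boundary at Visit 16 for rollover subjects.** In SAP 9.9.1 the double-blind window runs to "the first dose of study drug during the Open-Label Extension for subjects who rolled over" directly. The Main Study window runs "up to the first day of the Open-Label Extension period for rollover subjects". The Open-Label Extension (OLE) window is "on or after the first dose of Open-Label study drug during the Open-Label Extension period up to the last dose of study drug + 30 days". SAP 3.1.2 makes Visit 16 both the final Main Study day and OLE Day 1 for these subjects.

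**What the plan does elsewhere.** The note to SAP Table 1 says "Period Day 1 is excluded from the visit windows as the study drug will be taken only after all the assessments scheduled" for that day have been done, and a note to Table 2 repeats the exclusion. Protocol 9.11.1 counts an AE as treatment-emergent if it begins or worsens after the first dose, and limits period summaries to events emergent in that period. SAP 3.6 lists only the BOCF imputation as a departure from the protocol.

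**The concern.** In a randomized-withdrawal trial, the hours before the first blinded dose are active-drug hours for everyone. An event in the daytime of Visit 15 arose on open-label JZP-258 whichever arm the subject was assigned to that day. If emergence is settled by date, the event enters the double-blind tables, and for half the subjects it enters the placebo column. That blurs the only randomized safety comparison in the trial.

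There may be a second consequence. SAP 9.9 removes data collected on placebo from the all-period safety summaries. If that removal follows the same date window, a Visit 15 event that arose on JZP-258 in a placebo subject would also disappear from the all-period JZP-258 tables.

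At Visit 16 the problem is overlap. That visit includes a physical examination, an ECG and fasting laboratory tests, and clinically significant adverse changes are AEs under Protocol 6.13.1. A finding made after two weeks on placebo could be shown both as a double-blind placebo event and as an OLE JZP-258 event.

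**Working it through.** The documents give no figure to reproduce here. The check is to apply the windows date by date and compare the result with the treatment in force.

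**Inputs**
- Day 1 is the date of Visit 15, with the first double-blind dose at bedtime that day (Protocol 5.2 and 7.1.4; SAP 6.1).
- Day 15 is the date of Visit 16, with the first OLE dose at bedtime for rollover subjects (SAP 3.1.2 and Table 1).
- Emergence is decided by date with equality counted (SAP Appendix 2), and the closing limits in SAP 9.9.1 are read as inclusive.

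**Rollover subject, event in the daytime**

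| Date | Treatment in force | Windows met |
|---|---|---|
| Day 0 | open-label JZP-258 | Main Study |
| Day 1 (Visit 15) | open-label JZP-258 | double-blind, Main Study |
| Days 2 to 14 | blinded drug | double-blind, Main Study |
| Day 15 (Visit 16) | blinded drug | double-blind, Main Study, OLE |
| Day 16 | OLE JZP-258 | OLE |

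Only Days 1 and 15 go wrong. On Day 1 the period is wrong. On Day 15 the event meets both the double-blind/Main Study definitions and the OLE definition.

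**Share of the window**
- Rollover subject, Days 1 to 15: 1/15 = 6.7%.
- Window closing with a last dose dated Day 14: 1/14 = 7.1%.

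**How much of Day 1 precedes the blinded dose** (assuming a first dose between 21:00 and 23:00)
- 21/24 = 87.5%; 23/24 = 95.8%.

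**Illustrative count** (the documents give no daily AE rate; 0.01 to 0.05 onsets per subject-day is an assumption)
- 65 subjects × 1 day × 0.01 = 0.65 events per arm.
- 65 × 1 × 0.05 = 3.25 events per arm.
- The upper rate implies 14 × 0.05 = 0.7 new events per subject over two weeks.

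**The case against.** The strongest reply is that SAP 9.9.1 refers to a dose, not a dose date. Read literally, an event before the bedtime dose is outside the double-blind window. The date inequality sits in an appendix on partial dates, and its 30-day tail matches the overall TEAE definition rather than the double-blind one. The eCRF is not in the documents, so onset times may be collected. This stands in part: date-level use for the double-blind window is an inference. But Appendix 2 is the only emergence algorithm given, it covers fully known start dates, and no rule uses an onset time.

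Other limits also stand:
- Some Groups 1 and 2 subjects may begin dosing after the first nightly awakening. A first dose after midnight carries the next day's date, and the problem does not arise.
- Randomized subjects have been on an unchanged dose for at least four weeks, without clinically significant JZP-258 AEs in the Stable-Dose Period, so a high event rate is doubtful. The documents do not show that AE onsets cluster on clinic dates.
- Safety analyses are descriptive, and every AE is listed.

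A reader might infer that the convention favours JZP-258. The documents do not support that: events before the first blinded dose are balanced between arms in expectation, so they dilute the contrast.

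A reader might also infer that every rollover event dated Visit 16 is counted twice in one table. That does not follow. The overlap needs an inclusive closing limit and date-only comparison, and the repeat is across separate period tables. The overall summary is a single window, and SAP 9.9.1.1 counts a subject once per SOC or preferred term.

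Finally, excluding the first-dose day from every period would do harm. Protocol 5.2 puts sedative effects at 2 to 4 hours, so a placebo subject restarting JZP-258 after Visit 16 could react before midnight. An untimed reaction would then move into the placebo period. For re-entry subjects, SAP 9.9.1 classes events between the last double-blind and first OLE doses as post AEs, which are not summarized. This objection stands, and the fix is limited accordingly.

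**Conclusion.** The concern holds as a missing same-day rule. Applied at the date resolution of Appendix 2, SAP 9.9.1 places Visit 15 events that arose on open-label JZP-258 in the double-blind tables, including the placebo column. It also lets a rollover event dated Visit 16 appear in both the double-blind/Main Study and OLE tables. The first result conflicts with Protocol 9.11.1 and is inconsistent with the Day 1 exclusion in SAP 6.3.

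The effect is small: one of 14 to 15 dates, about 7% of the window, in descriptive safety only. No efficacy or sample-size figure changes. The conclusion assumes date-level comparison, a first dose before midnight on the visit date and, for Visit 16, inclusive closing limits. The 0.65 to 3.25 events per arm is an illustration from an assumed rate, not an estimate. Loss of Visit 15 events from the all-period JZP-258 tables is possible, but depends on how the placebo-data exclusion in SAP 9.9 is programmed.

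**What to change.** State the tie-breaks in SAP 9.9.1 and Appendix 2:

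1. **Double-blind opening.** Assign an AE dated on the first double-blind dose date to the open-label period unless a recorded onset time is after that dose. Use the same boundary for the placebo-data exclusion in SAP 9.9.
2. **Visit 16, rollover subjects.** Make the double-blind/Main Study windows and the OLE window mutually exclusive. Use onset time relative to the first OLE dose where recorded. Assign findings from pre-dose Visit 16 assessments to the double-blind period. Keep other untimed events of that date in the OLE, so that first-night JZP-258 reactions are not moved to placebo.
3. **Unchanged.** Keep the on-or-after wording for Study Day 1 and for re-entry subjects at Visit 19.

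The cost is a short SAP edit and its programming, best settled before unblinding. The downside is that an untimed AE starting between the first double-blind bedtime dose and midnight stays in the open-label period. Little is lost, because no new active drug starts that night in either arm.
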